#### **CONTRACEPTION GUIDANCE FOR MALE PARTICIPANTS WITH PARTNER(S) OF CHILD BEARING POTENTIAL.**

Male participants with female partners of childbearing potential are eligible to participate if they agree to the following during the treatment and until the end of relevant systemic exposure.

- Inform any and all partner(s) of their participation in a clinical drug study and the need to comply with contraception instructions as directed by the investigator.
- Male participants are required to use a condom for study duration and until end of relevant systemic exposure defined as 7 months after the end of study treatment.
- Female partners of males participating in the study to consider use of effective methods of contraception until the end of relevant systemic exposure, defined as 7 months after the end of treatment in the male participant.
- Male participants with a pregnant or breastfeeding partner must agree to remain abstinent from penile vaginal intercourse or use a male condom during each episode of penile penetration during the treatment and until 7 months after the end of study treatment.
- Refrain from donating sperm for the duration of the study treatment and until 7 months after the end of study treatment.

#### **COLLECTION OF PREGNANCY INFORMATION**

Guidance for collection of Pregnancy Information and outcome of pregnancy on the Pregnancy Surveillance Form is provided in [Section 9.2.5](#) and the Appendix for Adverse Events and Serious Adverse Events Definitions and procedures for Evaluating, Follow-up and Reporting

## APPENDIX 5 ECOG PERFORMANCE STATUS

ECOG PERFORMANCE STATUS a	
0	Fully active, able to carry on all pre-disease performance without restriction
1	Restricted in physically strenuous activity but ambulatory and able to carry out work of a light or sedentary nature, eg, light house work, office work
2	Ambulatory and capable of all selfcare but unable to carry out any work activities. Up and about more than 50% of waking hours
3	Capable of only limited selfcare, confined to bed or chair more than 50% of waking hours
4	Completely disabled. Cannot carry on any selfcare. Totally confined to bed or chair
5	Dead

a Oken MM, Creech RH, Tormey DC, Horton J, Davis TE, McFadden ET, and Carbone PP. Toxicity and Response Criteria of the Eastern Cooperative Oncology Group. Am J Clin Oncol 1982; 5: 649-655.

## **APPENDIX 6 RECIST 1.1 GUIDELINES**

### **1 EVALUATION OF LESIONS**

At baseline, tumor lesions/lymph nodes will be categorized measurable or non-measurable as follows:

#### **1.1 Measurable**

Tumor lesions: Must be accurately measured in at least one dimension (longest diameter in the plane of measurement is to be recorded) with a minimum size of:

1. 10 mm by CT scan (CT scan slice thickness no greater than 5 mm)
2. 10 mm caliper measurement by clinical exam (lesions which cannot be accurately measured with calipers should be recorded as non-measurable)
3. 20 mm by chest x-ray

*Malignant lymph nodes:* To be considered pathologically enlarged and measurable, a lymph node must be  $\geq 15$  mm in short axis when assessed by CT scan (CT scan slice thickness recommended to be no greater than 5 mm).

Lymph nodes merit special mention since they are normal anatomical structures which may be visible by imaging even if not involved by tumor. Pathological nodes which are defined as measurable and may be identified as target lesions must meet the criterion of a short axis of  $\geq 15$  mm by CT scan. Only the short axis of these nodes will contribute to the baseline sum. The short axis of the node is the diameter normally used by radiologists to judge if a node is involved by solid tumor. Nodal size is normally reported as two dimensions in the plane in which the image is obtained (for CT scan this is almost always the axial plane; for MRI the plane of acquisition may be axial, sagittal or coronal). The smaller of these measures is the short axis. For example, an abdominal node which is reported as being 20 mm x 30 mm has a short axis of 20 mm and qualifies as a malignant, measurable node. In this example, 20 mm should be recorded as the node measurement. All other pathological nodes (those with short axis  $\geq 10$  mm but  $< 15$  mm) should be considered non-target lesions. Nodes that have a short axis  $< 10$  mm are considered non-pathological and should not be recorded or followed.

#### **1.2 Non-Measurable**

All other lesions are considered non-measurable, including small lesions (longest diameter  $< 10$  mm or pathological lymph nodes with  $\geq 10$  to  $< 15$  mm short axis) as well as truly non-measurable lesions. Lesions considered truly non-measurable include: leptomeningeal disease, ascites, pleural or pericardial effusion, inflammatory breast disease, lymphangitic involvement of skin or lung, abdominal masses/abdominal organomegaly identified by physical exam that is not measurable by reproducible imaging techniques.

## **2           BASELINE DOCUMENTATION OF 'TARGET' AND 'NON-TARGET' LESIONS**

When more than one measurable lesion is present at baseline all lesions up to a maximum of five lesions total (and a maximum of two lesions per organ) representative of all involved organs should be identified as target lesions and will be recorded and measured at baseline (this means in instances where patients have only one or two organ sites involved a maximum of two and four lesions respectively will be recorded).

Target lesions should be selected on the basis of their size (lesions with the longest diameter), be representative of all involved organs, but in addition should be those that lend themselves to reproducible repeated measurements. It may be the case that, on occasion, the largest lesion does not lend itself to reproducible measurement in which circumstance the next largest lesion which can be measured reproducibly should be selected.

A sum of the diameters (longest for non-nodal lesions, short axis for nodal lesions) for all target lesions will be calculated and reported as the baseline sum diameters. If lymph nodes are to be included in the sum, then as noted above, only the short axis is added into the sum. The baseline sum diameters will be used as reference to further characterize any objective tumor regression in the measurable dimension of the disease.

All other lesions (or sites of disease) including pathological lymph nodes should be identified as non-target lesions and should also be recorded at baseline. Measurements are not required and these lesions should be followed as 'present', 'absent', or in rare cases 'unequivocal progression' (more details to follow). In addition, it is possible to record multiple nontarget lesions involving the same organ as a single item on the case record form (eg, 'multiple enlarged pelvic lymph nodes' or 'multiple liver metastases').

## **3           RESPONSE CRITERIA**

### **3.1       Evaluation of Target Lesions**

**Complete Response (CR):** Disappearance of all target lesions. Any pathological lymph nodes (whether target or non-target) must have reduction in short axis to < 10 mm.

**Partial Response (PR):** At least a 30% decrease in the sum of diameters of target lesions, taking as reference the baseline sum diameters.

**Progressive Disease (PD):** At least a 20% increase in the sum of diameters of target lesions, taking as reference the smallest sum on study (this includes the baseline sum if that is the smallest on study). In addition to the relative increase of 20%, the sum must also demonstrate an absolute increase of at least 5 mm. (Note: the appearance of one or more new lesions is also considered progression).

**Stable Disease (SD):** Neither sufficient shrinkage to qualify for PR nor sufficient increase to qualify for PD, taking as reference the smallest sum diameters while on study.

### **3.1.1      *Special Notes on the Assessment of Target Lesions***

#### **3.1.1.1    *Lymph nodes***

Lymph nodes identified as target lesions should always have the actual short axis measurement recorded (measured in the same anatomical plane as the baseline examination), even if the nodes regress to below 10 mm on study. This means that when lymph nodes are included as target lesions, the ‘sum’ of lesions may not be zero even if complete response criteria are met, since a normal lymph node is defined as having a short axis of < 10 mm. Case report forms or other data collection methods may therefore be designed to have target nodal lesions recorded in a separate section where, in order to qualify for CR, each node must achieve a short axis < 10 mm. For PR, SD and PD, the actual short axis measurement of the nodes is to be included in the sum of target lesions.

#### **3.1.1.2    *Target lesions that become ‘too small to measure’***

While on study, all lesions (nodal and non-nodal) recorded at baseline should have their actual measurements recorded at each subsequent evaluation, even when very small (eg, 2 mm). However, sometimes lesions or lymph nodes which are recorded as target lesions at baseline become so faint on CT scan that the radiologist may not feel comfortable assigning an exact measure and may report them as being ‘too small to measure’. When this occurs it is important that a value be recorded on the case report form. If it is the opinion of the radiologist that the lesion has likely disappeared, the measurement should be recorded as 0 mm. If the lesion is believed to be present and is faintly seen but too small to measure, a default value of 5 mm should be assigned (Note: It is less likely that this rule will be used for lymph nodes since they usually have a definable size when normal and are frequently surrounded by fat such as in the retroperitoneum; however, if a lymph node is believed to be present and is faintly seen but too small to measure, a default value of 5 mm should be assigned in this circumstance as well). This default value is derived from the 5 mm CT slice thickness (but should not be changed with varying CT slice thickness). The measurement of these lesions is potentially non-reproducible, therefore providing this default value will prevent false responses or progressions based upon measurement error. To reiterate, however, if the radiologist is able to provide an actual measure, that should be recorded, even if it is below 5 mm.

#### **3.1.1.3    *Lesions that split or coalesce on treatment***

When non-nodal lesions ‘fragment’, the longest diameters of the fragmented portions should be added together to calculate the target lesion sum. Similarly, as lesions coalesce, a plane between them may be maintained that would aid in obtaining maximal diameter measurements of each individual lesion. If the lesions have truly coalesced such that they are no longer separable, the vector of the longest diameter in this instance should be the maximal longest diameter for the ‘coalesced lesion’.

## **3.2            *Evaluation of Non-Target Lesions***

This section provides the definitions of the criteria used to determine the tumor response for the group of non-target lesions. While some non-target lesions may actually be measurable, they need not be measured and instead should be assessed only qualitatively at the time points specified in the protocol.

**Complete Response (CR):** Disappearance of all non-target lesions and normalization of tumor marker level. All lymph nodes must be non-pathological in size (< 10mm short axis).

**Non-CR/Non-PD:** Persistence of one or more non-target lesion(s) and/or maintenance of tumor marker level above the normal limits.

**Progressive Disease (PD):** Unequivocal progression (see comments below) of existing non-target lesions. (Note: the appearance of one or more new lesions is also considered progression).

### **3.2.1      *Special Notes on Assessment of Progression of Non-Target Disease***

The concept of progression of non-target disease requires additional explanation as follows:

#### **3.2.1.1    *When the patient also has measurable disease***

In this setting, to achieve 'unequivocal progression' on the basis of the non-target disease, there must be an overall level of substantial worsening in non-target disease such that, even in presence of SD or PR in target disease, the overall tumor burden has increased sufficiently to merit discontinuation of therapy (see examples in [Appendix 2](#) and further details below). A modest 'increase' in the size of one or more non-target lesions is usually not sufficient to qualify for unequivocal progression status. The designation of overall progression solely on the basis of change in non-target disease in the face of SD or PR of target disease will therefore be extremely rare.

#### **3.2.1.2    *When the patient has only non-measurable disease***

This circumstance arises in some trials when it is not a criterion of study entry to have measurable disease. The same general concepts apply here as noted above, however, in this instance there is no measurable disease assessment to factor into the interpretation of an increase in non-measurable disease burden. Because worsening in non-target disease cannot be easily quantified (by definition: if all lesions are truly non-measurable) a useful test that can be applied when assessing patients for unequivocal progression is to consider if the increase in overall disease burden based on the change in non-measurable disease is comparable in magnitude to the increase that would be required to declare PD for measurable disease: ie, an increase in tumor burden representing an additional 73% increase in 'volume' (which is equivalent to a 20% increase diameter in a measurable lesion). Examples include an increase in a pleural effusion from 'trace' to 'large', an increase in lymphangitic disease from localized to widespread, or may be described in protocols as 'sufficient to require a change in therapy'. If 'unequivocal progression' is seen, the patient should be considered to have had overall PD at that point. While it would be ideal to have objective criteria to apply to non-measurable disease, the very nature of that disease makes it impossible to do so; therefore the increase must be substantial.

### **3.2.2      *New Lesions***

The appearance of new malignant lesions denotes disease progression; therefore, some comments on detection of new lesions are important. There are no specific criteria for the identification of new radiographic lesions; however, the finding of a new lesion should be unequivocal: ie, not attributable to differences in scanning technique, change in imaging modality or findings thought

to represent something other than tumor (for example, some ‘new’ bone lesions may be simply healing or flare of pre-existing lesions). This is particularly important when the patient’s baseline lesions show partial or complete response. For example, necrosis of a liver lesion may be reported on a CT scan report as a ‘new’ cystic lesion, which it is not.

A lesion identified on a follow-up study in an anatomical location that was not scanned at baseline is considered a new lesion and will indicate disease progression. An example of this is the patient who has visceral disease at baseline and while on study has a CT or MRI brain ordered which reveals metastases. The patient’s brain metastases are considered to be evidence of PD even if he/she did not have brain imaging at baseline.

If a new lesion is equivocal, for example because of its small size, continued therapy and follow-up evaluation will clarify if it represents truly new disease. If repeat scans confirm there is definitely a new lesion, then progression should be declared using the date of the initial scan.

### **3.3 Response Assessment**

#### ***3.3.1 Evaluation of Best Overall Response***

The best overall response is the best response recorded from the start of the study treatment until the end of treatment taking into account any requirement for confirmation. The patient’s best overall response assignment will depend on the findings of both target and non-target disease and will also take into consideration the appearance of new lesions. Furthermore, depending on the nature of the study and the protocol requirements, it may also require confirmatory measurement.

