**Table 2-4: Follow-Up and Survival Procedural Outline CA209592 (All Treatment Groups Part 1 and Part 2)**

Procedure	Follow-Up Visits 1 a & 2 b	Survival Follow-up Visits c	Notes
Safety Assessments			
Targeted Physical Examination	X		To assess for potential late emergent study drug related issues.
Vital Signs	X		
Adverse Events Assessment	X		Beyond 100 days from the last dose of study drug, participants will be followed for ongoing drug-related adverse events until resolved, return to baseline or deemed irreversible, or until lost to follow-up, withdrawal of study consent, or start of subsequent therapy.
Laboratory Tests	X		To be done at FU1, to be repeated at FU2, if study related toxicity persists. CBC w/ differential, LFTs, BUN or serum urea level, creatinine, Ca, Mg, Na, K, Cl, Phosphorus, LDH, Glucose, amylase, lipase. If TSH is abnormal, then TSH with reflexive Free T4, Free T3 is to be performed
Pregnancy Test (WOCBP Only)	X		Section 9.2.5.
Efficacy Assessments			
Radiographic Tumor Assessments	X		For participants who discontinue study treatment for reasons other than radiographic PD, follow-up scans should continue to be performed according to the on-study assessment schedule ( Table 2-2 and Table 2-3 ) until PD, withdrawal of consent, or start of subsequent therapy, death, or lost to follow-up After 3 years on study, tumor assessments for long-term survivors can be performed at a frequency per institutional guidelines or every 24 weeks based on NCCN surveillance guidelines.
Collection of Survival Status and Subsequent Therapy Information	X	X	Every 3 months after FU2; May be completed by office visit, phone contact or email, to assess subsequent anti-cancer therapy.

a Follow-up visit 1 (FU1) = 30 days from the last dose +/- 7 days or coincides with the date of discontinuation (+/- 7 days) if date of discontinuation is greater than 35 days after last dose.

b Follow-up visit 2 (FU2) = 100 days (+/- 7 days) from follow-up visit 1

c Every 3 months (+/- 7 days) from FU2

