**Table 4-2: Objectives and Endpoints for Part 2.**

Objectives	Endpoints
Primary	

To evaluate the association between baseline tissue TMB/bTMB and clinical efficacy (ORR) for participants in Part 2

	

The clinical efficacy will be measured by the analysis endpoint of objective response rate (ORR). The association of ORR with baseline tissue TMB and bTMB will be assessed

Secondary	

To investigate bacterially generated and human components enteric biomarkers and identify potential associations with clinical outcomes, including safety and efficacy for participants

	

ORR, PFS, OS

Incidence of AES, SAEs, and select AEs

- Objective response rate (ORR):** The proportion of patients with best overall response (BOR) of RECIST 1.1 defined confirmed complete response (CR) or partial response (PR) in a pre-defined study population.
- Disease control rate (DCR):** The proportion of patients with best overall response (BOR) of RECIST 1.1 defined complete response (CR), partial response (PR), or stable disease (SD) in a pre-defined study population
- Duration of response (DOR):** DOR is defined as the time between the date of the first confirmed response (CR/PR) to the date of the first documented tumor progression (per RECIST 1.1) or death due to any cause. Participants who neither progress nor die will be censored on the date of their last evaluable tumor assessment. Participants who started any subsequent anti-cancer therapy without a prior reported progression will be censored at the last evaluable tumor assessment prior to or on the date of initiation of subsequent anti-cancer therapy.

- **Time to response (TTR):** TTR is measured from the time of first dosing date to the time the criteria for CR/PR are first met.
- **Progression free survival (PFS):** PFS is defined as the time from first dosing date to the date of the first documented tumor progression (per RECIST) or death due to any causes. Participants who neither progress nor die will be censored on the date of their last evaluable tumor assessment. Participants who started any subsequent anti-cancer therapy without a prior reported progression will be censored at the last evaluable tumor assessment prior to or on the date of initiation of subsequent anti-cancer therapy.

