### **8.1.2 Disease Progression**

In general, study treatment must be discontinued at the time of disease progression per RECIST 1.1 criteria. However, accumulating evidence indicates a minority of subjects treated with immunotherapy may derive clinical benefit despite initial evidence of PD.

Participants may be permitted to continue study treatment with nivolumab (with or without ipilimumab) beyond initial investigator assessed RECIST 1.1 defined PD, upon approval by the BMS Medical Monitor or Study Director, as long as they meet the following criteria:

- Investigator-assessed clinical benefit.
- Tolerance of study therapy
- Stable performance status
- Treatment beyond progression will not delay an imminent intervention to prevent serious complications of disease progression (eg, CNS metastases)
- Participant provides written informed consent prior to receiving additional nivolumab treatment. All other elements of the main consent including description of reasonably foreseeable risks or discomforts, or other alternative treatment options will still apply.

Upon progression, a radiographic assessment/scan should be performed within 6 weeks of initial investigator-assessed progression to determine whether there has been a decrease/ limited change in the tumor size or continued PD. The assessment of clinical benefit should be balanced by clinical judgment as to whether the participant is clinically deteriorating and unlikely to receive any benefit from continued treatment with nivolumab.

If the investigator feels that the participant continues to achieve clinical benefit by continuing treatment (with or without ipilimumab), the participant should remain on the trial and continue according to the Schedule of Activities in [Section 2](#).

For participants who continue nivolumab (with or without ipilimumab) beyond progression, further progression is defined as an additional 10% increase in tumor burden with a minimum 5 mm absolute increase from time of initial PD. This includes an increase in the sum of diameters of all target lesions and/ or the diameters of new measurable lesions compared to the time of initial PD. Nivolumab treatment should be discontinued permanently upon documentation of further progression.

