#### **9.1.1.1 Efficacy Assessments using CT scan or MRI**

The imaging assessment schedule is provided in Table 9.1.1.1-1.

Baseline imaging is required within 28 days prior to first dose, including CT chest, CT/MRI abdomen, and pelvis (with contrast, unless contraindicated), plus any area that is being monitored.

Participants must have an MRI of the brain at screening. Participants with a history of brain metastasis should have surveillance MRI approximately every 12 weeks, or sooner if clinically indicated.

Tumor assessments should continue every 8 weeks ( $\pm$  1 week) from first dose for the first 12 months on treatment, then every 12 weeks ( $\pm$  1 week) until documented radiographic disease progression. CT chest and CT/MRI abdomen and pelvis (with contrast, unless contraindicated), plus any area that is being monitored. Use the same imaging method as was used at screening. After 3 years on study, tumor assessments for long-term survivors can be performed at a frequency per institutional guidelines or every 24 weeks based on NCCN surveillance guidelines.

In Part 1, an *additional planned optional CT scan is suggested at W5*, to guide tumor biopsy as needed and to support predicting tumor response based on early tumor growth characteristics using a mathematical tumor growth model.

For participants who discontinue study treatment for reasons other than radiographic PD, follow-up scans should continue to be performed according to the on-study assessment schedule until PD, withdrawal of consent, start of subsequent therapy, death, or lost to follow-up.

Participants who remain on therapy beyond initial progression, will have an assessment performed within 6 weeks to confirm progression (see [section 8.1.2](#)).

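### The only stated window for best overall response, which drives the primary ORR, ends at an undefined end of treatment: it omits responses first seen after a non-PD stop and, for the few treated past progression, admits responses after PD

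*Combined protocol and SAP*

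**What the plan says.** Section 4 (definitions under Table 4-2) builds the primary endpoint on BOR. ORR is "The proportion of patients with best overall response (BOR) of RECIST 1.1 defined confirmed complete response (CR) or partial response (PR") in a pre-defined population. No start or end of the assessment period is given there, and none appears in the visible text of Section 10.3.1.

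The period appears only in Appendix 6, section 3.3.1, where BOR is "the best response recorded from the start of the study treatment until the end of treatment taking into account any requirement for confirmation". End of treatment is not defined. Table 2-4, footnote a, treats last dose and discontinuation as separate dates: Follow-up Visit 1 "coincides with the date of discontinuation (+/- 7 days) if date of discontinuation is greater than 35 days after last dose".

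Other parts of the plan bear on the same window:

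- **Scans after a non-PD stop.** Section 9.1.1.1 says "follow-up scans should continue to be performed according to the on-study assessment schedule until PD", or until another listed event such as subsequent therapy. Tables 2-2, 2-3 and 2-4 repeat this. Section 9.1.1 also gathers unscheduled imaging that could show response, with no on-treatment limit.
- **Time to response.** "TTR is measured from the time of first dosing date to the time the criteria for CR/PR are first met".
- **Duration of response.** "DOR is defined as the time between the date of the first confirmed response (CR/PR) to the date of the first documented tumor progression", or death.
- **Subsequent therapy (DOR and PFS).** "Participants who started any subsequent anti-cancer therapy without a prior reported progression will be censored at the last evaluable tumor assessment" before or on the day that therapy starts.
- **Treatment beyond progression.** Section 8.1.2: "Participants may be permitted to continue study treatment with nivolumab (with or without ipilimumab) beyond initial investigator assessed RECIST 1.1 defined PD", subject to sponsor approval and listed criteria.

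Section 10.3 promises a SAP before database lock. A separate SAP is not among the documents supplied.

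**The concern.** The window in Appendix 6 is tied to drug exposure, whereas the scan schedule and the DOR and PFS rules are tied to progression and subsequent therapy. The two do not match, and ORR follows the exposure-based one.

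**(a) After a non-PD stop.** A participant who discontinues for toxicity and then shows a confirmed PR on required scans is a non-responder if Appendix 6 is followed.

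**(b) After progression.** A participant kept on treatment past RECIST PD is still inside the window, so a later PR can become the BOR although progression has already ended PFS.

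Responder status is the outcome in the logistic and ROC analyses of tissue and blood TMB (Section 10.3.1). What is at stake is whether two analysts with the same scans would classify the same people as responders. No formal hypothesis is tested (Sections 3.2.6 and 5.2), so no type I error rate is affected.

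**Working it through.** **1. Case (a), read side by side.** Take a participant who is discontinued for toxicity before the first scheduled on-study scan (Week 9 in Table 9.1.1.1-1) and has a PR on the next two scheduled scans.

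- Section 9.1.1.1: both scans are required.
- Appendix 6, 3.3.4: the second scan can confirm the first.
- Section 4, TTR: the response has a date.
- Appendix 6, 3.3.1: both scans fall after the end of treatment, so the BOR is not PR.

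The TTR definition is supportive rather than decisive, because Section 10.3.1 summarises TTR only in participants whose BOR is CR or PR.

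**2. Case (b), worked under Appendix 6.** Target-lesion sums of 100 (baseline), 125, 65 and 60 mm, no new lesions, non-target disease not progressing, treatment continued under Section 8.1.2, last two scans at least 28 days apart.

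- 125: (125 − 100)/100 = 25% above the smallest sum, and 25 mm absolute (at least 5 mm needed), so PD.
- 65: (100 − 65)/100 = 35% below baseline, so PR.
- 60: (100 − 60)/100 = 40% below baseline, so PR, confirming.

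Under 3.3.1 the BOR is PR. DOR would then run from the second or third on-study scan back to the first, which is negative. Table 3.3.3-1 has no row that starts with PD, so it does not settle the case.

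**3. Illustrative size of case (a), Part 2.** Inputs from the earlier study CA209012, cohort Q (nivolumab 3 mg/kg every 2 weeks plus ipilimumab 1 mg/kg every 6 weeks):

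- Stopped for drug-related adverse events: 5 of 39 = 12.8% (Table 3.2.2-1); exact 95% CI 4.3 to 27.4%.
- Confirmed ORR: 39% (23, 55) (Table 3.2.2-2). Check: 15/39 = 38.5%, Clopper-Pearson 23.4 to 55.4%, which matches.

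Assumptions, not in the documents: those who stop respond at the cohort rate of 39%, and 10% to 50% of those responses are first seen after discontinuation.

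- Stops: 150 × 5/39 = 19.2.
- Responders among them: 19.2 × 0.39 = 7.5.
- First seen after discontinuation: 7.5 × 0.10 = 0.75, up to 7.5 × 0.50 = 3.75 patients.
- ORR: 0.75/150 = 0.5 points, up to 3.75/150 = 2.5 points.

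The range reflects the assumed shares only, not the sampling error in 5/39. It omits non-PD stops for other reasons, so it is not a ceiling. The low end is likelier, because Section 5.6 says responses mostly come early, at a median of 2 to 4 months.

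**4. Scale.** An ORR of 58/150 = 38.7% has an exact 95% CI of 30.8 to 47.0%. Section 10.1 expects 250 × 60% × 1/3 = 50 TMB-positive participants over both Parts (reproduced). One reclassified patient there moves ORR by 1/50 = 2.0 points.

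**The case against.** **Appendix 6 is template text.** It is headed as general RECIST guidance and covers situations that cannot arise here, such as participants with no measurable disease. The study-specific sections set no on-treatment limit and suggest that off-treatment scans were meant to count. That is a fair reading of intent. But the sentence is still the only window stated, and nothing says the body text overrides it.

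**The SAP may define the window.** It may, and parts of Section 10 are redacted. This point therefore concerns the visible text only. A SAP with a different window would still leave Appendix 6 to be aligned.

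**Case (b) is narrow.** This stands. Treatment stops at PD by default. Any time point with a new lesion is PD (Table 3.3.2-1). Equivocal progression not confirmed on repeat is not PD (3.3.4). Disease that reappears after a true CR is PD (Table 3.3.3-1, footnote a). The DOR definition also presumes that response comes before progression. What remains is a clear target-lesion PD followed by a PR without new lesions, and no visible rule keeps that out of BOR.

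**Stronger readings a reader might infer, and why they fail:**

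- *Every response seen off drug is lost.* Dosing may be held for weeks with scans continuing (Sections 7.4.1 and 8.1.1). If end of treatment means the discontinuation date, a response seen during a hold still counts. Only those first seen after discontinuation are excluded on either reading.
- *Off-drug confirmation of an on-drug response is barred.* Section 3.3.4 accepts the next scheduled scan, and Section 9.1.1.1 keeps the schedule running, so it is admitted by implication.
- *All non-PD stops give the size.* Cohort Q had 39 − 7 on treatment − 20 stopped for PD = 12. Then 150 × 12/39 = 46.2, and the same shares give 1.8 to 9.0 patients (1.2 to 6.0 points). But those stops accrued over a median 51.1 weeks, late stoppers have mostly responded already or will not, and the 12 may include deaths and withdrawals without later scans.
- *The roughly 10% in Section 3.2.4 sizes case (b).* That figure comes from other studies, includes stable disease after progression, and does not separate cases with new lesions.

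**Conclusion.** Wrong as written, and modest in size. Followed literally, the one visible BOR window misclassifies some responders on the primary endpoint, and its end date is undefined.

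For case (a), about 0.75 to 3.75 of 150 Part 2 patients (0.5 to 2.5 ORR points) is an illustration. It rests on cohort Q's stopping rate carrying over, a 39% response rate among those who stop, and an unsourced 10% to 50% share first seen after discontinuation. For case (b), the documents support no figure.

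The two faults pull in opposite directions: (a) lowers ORR and (b) can raise it. They affect different participants, so cancellation cannot be assumed. The documents do not support a reading that the ORR result is materially biased or that a test is invalidated. The harm is to consistent, reproducible classification. It should be fixed because the remedy is simple and responder status is the outcome in the TMB analyses.

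**What to change.** Change the analysis definition only. State the following in Section 4, Section 10.3.1 and Appendix 6 section 3.3.1, and repeat it in the SAP:

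*BOR is the best response recorded from first dose until the earlier of first RECIST 1.1-defined progression or start of subsequent anti-cancer therapy, whether or not the participant is still on study treatment. Equivocal progression not confirmed on a repeat scan does not close the window. The confirming scan must be at least 4 weeks later and must also fall within the window.*

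Use this window for ORR, DCR and TTR. Leave the DOR and PFS rules as they are. Report responses after RECIST progression separately, as descriptive results.

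The cost is one short definition placed consistently. No scans are added, because imaging after a non-PD stop is already scheduled until progression or subsequent therapy. No treatment rule changes.
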